5.1.12 Pharmacokinetic Assessments

Blood samples for determination of sebelipase alfa serum concentrations will be collected during the study visits indicated in Appendix A. On each PK visit, samples will be collected at the following timepoints relative to infusion of IMP:

• Immediately pre-dose (within 30 minutes of dosing)

Page 32 of 76

- At 10(±1), 15(±1), 20(±1), 40(±5), 60(±5) and 90(±5) minutes during the infusion and at the end of the infusion
- At 5(±1), 10(±1), 20(±1), 30(±5), 40(±5), 60(±5) and 120(±5) minutes after completion of the infusion

All PK samples will be taken from the arm opposite the infusion cannula. PK samples scheduled for the same nominal timepoint as a vital sign assessment will be taken prior to cuff inflation for the blood pressure measurement. All other PK samples will be taken at least 5 minutes after cuff deflation.

Refer to the SOM and/or laboratory manual for further details regarding the collection, processing, and storage of these samples.

5.1.13 Liver Biopsy

As is the case with many rare metabolic chronic liver diseases, there is paucity of available information regarding the histopathological features of LAL Deficiency. Long term dosing in the pre-clinical disease model is associated with marked improvement in liver pathology. At present there is no information on the long term effects of sebelipase alfa on liver pathology in humans. Although baseline assessment of liver histology was not performed, information on liver histology after longer term dosing may provide useful information about the effects of sebelipase alfa in patients with late onset LAL Deficiency.

Optional liver biopsies will be obtained for evaluation of hepatic histology between Week 52 and Week 104. If a subject had a liver biopsy within 3 years prior to screening as part of clinical standard of care and the results of that biopsy are available, these results should be recorded in the eCRF. In addition, slides or scanned images from these biopsies should be submitted for evaluation by a central pathologist, if possible. Biopsies will be performed only with consent from the subject and where local regulations permit, and are subject to discretionary approval from each center's IRB/IEC.

Liver biopsy procedures should be performed according to the local institutional practices by a qualified professional.

All biopsies collected in this study will be centrally evaluated by a pathologist with the appropriate expertise. This evaluation will include an assessment of the overall disease activity as well as a description of specific histopathological features of the disease.

Refer to the Histopathology Manual for further details on the collection and processing of liver biopsies.

6 Treatments

6.1 Treatments Administered

Subjects will receive repeat IV infusions of sebelipase alfa, beginning at least 4 weeks after their last dose in study LAL-CL01 and continuing for approximately 5 years.

Each subject will initiate treatment at the same once-weekly dose of sebelipase alfa that he/she received during the fourth infusion in study LAL-CL01 (i.e., 0.35 mg/kg qw, 1 mg/kg qw, or 3 mg/kg qw), and will transition to a qow dosing regimen at Week 6 as described in Section 3.1.

At any time during the extension study, a subject may choose to transfer to a local medical center to receive their IMP infusions. Scheduled study assessments may also be performed at the local medical center provided that the center has access to the appropriate facilities and expertise.

6.1.1 Dose Escalation

After a minimum of 12 weeks of treatment in study LAL-CL04, a subject may be considered for a dose escalation, either from 1 mg/kg qow to 3 mg/kg qow or from 3 mg/kg qow to 3 mg/kg qw, if the subject exhibits an inadequate clinical response (see below). Prior to considering a dose increase, the subject should be evaluated for other potential causes of any clinical manifestations that are thought to reflect a suboptimal response. Other causes could include:

- missed study infusions,
- development of a new intercurrent illness, with the potential to confound the interpretation of biochemical efficacy measures, e.g.,
 - development of viral or autoimmune hepatitis or other alternative etiology of liver disease,
 - initiation of a potentially hepatotoxic concomitant medication in a subject with elevated ALT
 - initiation or modification of concomitant medication known to impact serum lipid levels.

Inadequate clinical response is defined as:

- Clinically important manifestations of LAL Deficiency on either clinical examination, laboratory assessment, liver biopsy or imaging which have either
 - a. not improved from baseline,
 - b. improved and plateaued but have not normalized,
 (Note: The definition of a plateauing of effect requires consideration of a minimum of 3 assessments.)
 - c. failed to normalize within 12 months of initiation of treatment.

Manifestations include but are not restricted to the following: elevated hepatic transaminases, abnormal liver function or coagulation tests, dyslipidemia, hepatomegaly, splenomegaly, significant histological abnormalities of the liver, or lymphadenopathy.

6.1.2 Dose Reduction

Subjects who do not tolerate their current dose level may receive a dose reduction to the next lowest dose level, i.e., 1 mg/kg qow or 0.35 mg/kg qow, at the discretion of the Investigator in consultation with the Sponsor and, where appropriate, the SC.

If a subject cannot tolerate a dose of 0.35 mg/kg qow, despite measures taken to manage any IARs, the subject will be discontinued from the study.

NOTE: Any subject who undergoes a dose modification, as described above, will have additional laboratory monitoring schedule of selected analytes, as detailed in Section 5.1.10.

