Main Inclusion and Criteria for	 Subject understands the full nature and purpose of the study, including possible risks and side effects, and is willing and able to comply with all study procedures and provide informed consent. Subject received all 4 scheduled doses of sebelipase alfa in study LAL-CL01 with no life-threatening or unmanageable study drug toxicity. Female subjects have a negative serum pregnancy test at screening, and are not breast-feeding. Female subjects of childbearing potential are willing and able to use a highly effective and approved contraceptive method(s) from the date of informed consent until 30 days after last dose of IMP.
Evaluation	A subject who meets any of the following exclusion criteria will be ineligible for this study:
	 Clinically significant concurrent disease, serious inter-current illness, concomitant medications, or other extenuating circumstances that, in the opinion of the Investigator, would interfere with study participation or the interpretation of the effects of sebelipase alfa. Clinically significant abnormal values on screening laboratory tests, other than liver function or lipid panel tests. Subjects with an abnormal laboratory value that is of borderline significance may be allowed to undergo repeat testing once within a 30-day period.
	Sebelipase alfa (SBC-102), a recombinant human lysosomal acid lipase (rhLAL) produced in the transgenic Gallus , will be administered by IV infusion. The following dosing regimens of sebelipase alfa may be administered in this study: 0.35 mg/kg qw, 1 mg/kg qw, 3 mg/kg qw, 1 mg/kg qow, and 3 mg/kg qow.
Investigational Medicinal Product, Dose, Route, Regimen	Subjects will initiate treatment in the extension study at least 30 days after their last dose of sebelipase alfa in study LAL-CL01. Each subject will initiate treatment in the extension study at the same once-weekly dose of sebelipase alfa that he/she received during the fourth infusion in study LAL-CL01, i.e., 0.35 mg/kg qw, 1 mg/kg qw, or 3 mg/kg qw. Subsequent modifications to the dose and dosing frequency will be undertaken for individual subjects as outlined below based on observed safety and tolerability and clinical response to treatment. All such decisions will be made jointly by the Investigator and Sponsor:

Page **5** of **76**

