	 At Week 6 (and after at least 4 infusions in the extension study), subjects receiving a starting dose of 0.35 mg/kg qw or 1 mg/kg qw will have their dose changed to 1 mg/kg qow. Similarly, subjects who were receiving a starting dose of 3 mg/kg qw for the first 4 infusions will transition to the 3 mg/kg qow regimen. After Week 12, subjects receiving a dose of 1 mg/kg qow may have their dose increased to 3 mg/kg qow based on observed safety and tolerability and/or clinical response to treatment.
	 After Week 12, subjects receiving a dose of 3 mg/kg qow may be considered for a dose adjustment to 3 mg/kg qw based on observed safety and tolerability and/or clinical response to treatment.
	 In the event of poor tolerability at any time during the extension study, the dose may be reduced at the discretion of the Investigator. If a subject cannot tolerate the lowest starting dose (0.35 mg/kg qw) despite measures taken to manage any IARs, he/she will be discontinued from treatment.
Duration of IMP administration	The duration of each subject's treatment in the study will vary but is expected to be at least 26 weeks and approximately 5 years.
Reference therapy	No reference therapy will be administered in this study.
	Safety The primary safety endpoints will include the incidence of adverse events (AEs) SAEs, and IARs; changes in vital signs (blood pressure, heart rate, respiratory rate, and temperature), physical examination findings, 12-lead electrocardiogram (ECG) parameters, and clinical laboratory tests (CBC/hematology, serum chemistry and urinalysis); use of concomitant medications/therapies; and characterization of anti-sebelipase alfa anti-drug antibodies (ADAs), including ADA positive rate, time to ADA positivity, peak ADA titer, and time to peak ADA titer. The effect of ADAs on the safety of sebelipase alfa will also be explored. A further characterization of ADAs, including inhibitory ADAs, may be performed as a separate pooled analysis across studies, and will be reported separately from this protocol.

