- In the event of poor tolerability at any time during the extension study, the dose may be reduced at the discretion of the Investigator. If a subject cannot tolerate the lowest starting dose (0.35 mg/kg qow) despite measures taken to manage any IARs, he/she will be discontinued from treatment.

Safety, tolerability, and efficacy assessments will be conducted at regular intervals throughout the extension study. In addition, blood samples will be obtained at selected timepoints for analysis of sebelipase alfa PK and biomarkers of sebelipase alfa PD activity. Blood samples will also be collected for an exploratory analysis of potential disease-related biomarkers in this patient population, and HRQOL measures will be assessed through subject questionnaires.

A follow-up visit will be conducted for all subjects at 30 (+7) days after the last dose of IMP.

Page 22 of 76

*After Week 12, a dose adjustment from 1 mg/kg qow to 3 mg/kg qow, or from 3 mg/kg qow to 3 mg/kg qw, may be considered based on safety and tolerability and/or clinical response to treatment. A dose reduction is permitted at any time in the event of poor tolerability.

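### The dose-reduction rules contradict each other on the permitted regimens, the tolerability floor and what follows from failing it, and the step-down term is undefined

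*Protocol*

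**What the plan says.** **Permitted regimens.** The synopsis (Investigational Medicinal Product, Dose, Route, Regimen) says which regimens "may be administered in this study: 0.35 mg/kg qw, 1 mg/kg qw, 3 mg/kg qw, 1 mg/kg qow, and 3 mg/kg qow".

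**Reduction.** Protocol 6.1.2 says that a subject who does not tolerate the current level "may receive a dose reduction to the next lowest dose level, i.e., 1 mg/kg qow or 0.35 mg/kg qow".

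**Escalation.** Protocol 6.1.1 describes dose escalation as "either from 1 mg/kg qow to 3 mg/kg qow or from 3 mg/kg qow to 3 mg/kg qw".

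**Floor.** There are four statements:
- Synopsis: "If a subject cannot tolerate the lowest starting dose (0.35 mg/kg qw"), the subject is discontinued from treatment.
- Protocol 3.1: "If a subject cannot tolerate the lowest starting dose (0.35 mg/kg qow"), the subject is discontinued from treatment.
- Protocol 6.1.2: "If a subject cannot tolerate a dose of 0.35 mg/kg qow, despite measures taken to manage any IARs", the subject is discontinued from the study.
- SAP 3.1: the floor is 0.35 mg/kg qw, and the subject is discontinued from treatment.

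**Who decides.** The synopsis and Protocol 3.1 introduce the list of dose changes by saying that such decisions are joint between Investigator and Sponsor. Within that list, the reduction item says that "the dose may be reduced at the discretion of the Investigator". Section 6.1.2 keeps the Investigator's discretion but adds consultation with the Sponsor and, where appropriate, the Safety Committee.

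**The concern.** A reduction rule has to tell a site four things: which regimens exist, which one comes next, when there is nothing lower to try, and what happens then. Here each answer depends on the section consulted.

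The study's primary objective is long-term safety and tolerability, so reductions and tolerability discontinuations are part of what it measures. With at most 9 subjects, one subject handled under a different reading is at least 1/9 = 11% of the sample. A subject who fails at 0.35 mg/kg qw is stopped under one section and may still be reduced under another. The status of 0.35 mg/kg qow also matters by the protocol's own account: Section 1.5.1 says the nonclinical data suggest a lower chance of showing efficacy with qow doses below 1 mg/kg. That remark does not settle which passage is right.

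**Working it through.** The documents state no percentage reduction, so there is no figure of theirs to reproduce. The check compares the sections and converts each regimen to an average weekly dose.

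**Step 1: weekly dose.** Weekly dose = mg/kg per infusion ÷ interval in weeks (qw = 1, qow = 2).

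| Regimen | Weekly dose (mg/kg) | On the synopsis list? |
|---|---|---|
| 3 mg/kg qw | 3 ÷ 1 = 3.0 | yes |
| 3 mg/kg qow | 3 ÷ 2 = 1.5 | yes |
| 1 mg/kg qw | 1 ÷ 1 = 1.0 | yes |
| 1 mg/kg qow | 1 ÷ 2 = 0.5 | yes |
| 0.35 mg/kg qw | 0.35 ÷ 1 = 0.35 | yes |
| 0.35 mg/kg qow | 0.35 ÷ 2 = 0.175 | **no** |

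The one regimen missing from the list is both a named reduction target and the floor in 6.1.2.

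**Step 2: the floor.**

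| Place | Floor | Consequence |
|---|---|---|
| Synopsis | 0.35 mg/kg qw | leaves treatment |
| Protocol 3.1 | 0.35 mg/kg qow | leaves treatment |
| Protocol 6.1.2 | 0.35 mg/kg qow | leaves the study |
| SAP 3.1 | 0.35 mg/kg qw | leaves treatment |

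The two floors differ by 0.35 ÷ 0.175 = 2-fold in weekly dose. Protocol 3.1 also calls its qow floor a starting dose, although Protocol 6.1 gives every starting dose as weekly (0.35, 1 or 3 mg/kg qw).

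**Step 3: the step down from 3 mg/kg qw.** Change = new weekly dose ÷ old weekly dose − 1.
- To 3 mg/kg qow (6.1.1 read in reverse): 1.5 ÷ 3.0 − 1 = −50.0%.
- To 1 mg/kg qow (named in 6.1.2): 0.5 ÷ 3.0 − 1 = −83.3%.
- To 0.35 mg/kg qow (named in 6.1.2): 0.175 ÷ 3.0 − 1 = −94.2%.

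Per infusion, the same three changes are 0%, 1 ÷ 3 − 1 = −66.7% and 0.35 ÷ 3 − 1 = −88.3%.

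**Step 4: does another section settle it?** Protocol 7.6 refers to Appendix E for dose modification. Appendix E covers stopping for severe infusion reactions and allows dosing to resume with alterations, but gives no reduction steps, no regimen list and no floor.

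**The case against.** The strongest objection concerns the escalation ladder. The protocol's own term for dose plus frequency is *dosing regimen* (Section 8.1), and Section 3.1 calls the move from 1 to 3 mg/kg qow an increase but the move from 3 mg/kg qow to qw an adjustment. If *dose level* means mg/kg per infusion, 6.1.2 gives a coherent sequence of 3, 1 and 0.35 with no step missing. The 50% figure comes only from reversing an escalation rule and is not a reduction written anywhere. This stands in part: the clash with the ladder depends on the reading. However, the term is undefined, 6.1.1 counts a change of frequency alone as an escalation, and 6.1.2 writes its own levels with a frequency attached. Both readings remain open.

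The objection does not reach the other conflicts. No meaning of *dose level* puts 0.35 mg/kg qow on the synopsis list, reconciles the two floors, or makes leaving treatment the same as leaving the study.

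A reader might infer two stronger points that the documents do not support:
- **That a reduction could be made without the Sponsor.** The synopsis and 3.1 place reductions under joint decisions, and 6.1.2 requires consultation with the Sponsor. What differs is the wording (discretion, joint decision, consultation) and whether the Safety Committee is mentioned.
- **That outcomes after a reduction could not be interpreted.** Adverse event listings carry the regimen before the event (Protocol 8.7.1), select listings carry the regimen at onset (SAP 5.1), and planned and actual volumes are listed for each infusion (SAP 11.1). With up to 9 subjects and no formal tests, these data can be read case by case.

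Reductions may also be few: Protocol 1.5.2 reports no SAEs or infusion-associated reactions in LAL-CL01. That lowers the likely impact but does not remove the contradiction.

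**Conclusion.** Wrong as written. Three contradictions are direct and need no assumption: 0.35 mg/kg qow is used but not permitted by the synopsis list; the floor is weekly in two places and every other week in two others; and the consequence is leaving treatment in three places and leaving the study in one.

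The fourth element is an ambiguity. For a subject on 3 mg/kg qw, the weekly dose falls by 50% if *dose level* means a regimen, and by 83% or 94% under the written list. The percentages assume that weekly dose is the relevant scale. The 50% further assumes that the ladder in 6.1.1 can be read downwards, so 50% against 83% should not be presented as two written rules in conflict.

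The effect is on consistency of conduct and on when an intolerant subject is reduced or stopped. Sample size follows LAL-CL01 enrollment, and no alpha or power is involved. Which regimen, floor or step is right is not for this review to say.

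**What to change.** Reconcile the synopsis (regimen list and dose-change items), Protocol 3.1, 6.1.1 and 6.1.2, and SAP 3.1, so that the following apply throughout:
- one list of permitted regimens;
- one definition of *dose level*, with an explicit step-down sequence from every permitted regimen;
- one tolerability floor;
- one consequence of failing it, stated as discontinuation of treatment or of the study;
- one wording on who authorises a reduction and when the Safety Committee is consulted.

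The sponsor decides the content of each. The cost is a protocol wording amendment and matching text in SAP 3.1, which only restates the protocol. No new data, assessments or analyses are needed.

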6.1.3 Home Infusions

Subjects who are in the maintenance phase of the study may be eligible to receive infusions at home, if appropriate, where infrastructure, resources, and procedures are established and available, allowed by local regulations, and approved by the Investigator and Sponsor.

To be considered for home infusions, a subject must have been on a stable dose of sebelipase alfa for at least 12 months and must meet all of the following criteria during the prior 6 months:

- No occurrences of IARs that required medical intervention or management;
- No SAEs determined to be related to IMP.

Subjects who are approved for home infusions will continue to return to the clinical site (or local medical center) for scheduled study assessments.

6.2 Description of IMP

Sebelipase alfa is a recombinant human lysosomal acid lipase produced in transgenic Gallus. Details of the nonclinical experience to date with sebelipase alfa, as well as IMP stability information, can be found in the current version of the Investigator Brochure (IB). Sebelipase alfa must be administered under close supervision of the Investigator, or designee.

Sebelipase alfa is provided in single dose 10 mL glass vials as a clear liquid. The solution (total 10.5 mL including 5% overfill) has an approximate concentration of 2 mg/mL.

Sebelipase alfa contains no preservatives and vials are single use only.

6.3 Method for Assigning Subjects to Treatment

No randomization schemes will be employed. All subjects will receive a starting dose equivalent to the dose of sebelipase alfa administered during their fourth infusion in study LAL-CL01. Subsequent modifications in dose and/or dosing frequency will be made in accordance with the protocol. See Section 3.1.

Subjects will retain the same subject number that they were assigned upon enrollment in study LAL-CL01. All IMP supply for the extension study will be linked to a unique active subject enrollment number.

6.4 Receipt, Storage, and Disposition of IMP

6.4.1 Receipt of IMP

Upon receipt of the IMP supplies, an inventory must be performed and a drug receipt log filled out and signed by the person accepting the shipment. It is important that the designated study staff counts and verifies that the shipment contains all the items noted in the shipment inventory. Any damaged or unusable IMP in a given shipment will be documented in the study files. The
Investigator must notify the Sponsor of any damaged or unusable IMP that was supplied to the Investigator's site.

6.4.2 Storage

Vials of IMP must be stored under controlled refrigerated conditions at 2 °C to 8 °C (36 °F to 46 °F). Vials should not be frozen and should be protected from light during storage.

The infusion bag containing sebelipase alfa should be prepared just prior to the start of infusion administration. Although the product in the infusion bag is stable at room temperature (23°C to 26°C) for up to 12 hours, the infusion should be initiated as soon as possible after preparation.

6.4.3 Disposition

The Investigator or designated person (e.g., a licensed pharmacist) will be responsible for maintaining accurate records for all supplies used. Opened sebelipase alfa vials still containing any residual volume may be stored at room temperature for IMP accountability. Following IMP accountability, the Sponsor will give written authorization to the Investigator to return or destroy any remaining IMP as instructed.

Under no circumstances will the IMP be used other than as directed in the protocol.

6.5 Preparation and Administration of IMP

6.5.1 Preparation of IMP

The subject's most recent protocol-scheduled weight measurement, rounded to the nearest 1.0 kg, will be used for calculating sebelipase alfa volume for each infusion. If a subject has a change in body weight of more than 10% during an interval between protocol-scheduled weight assessments, the unscheduled weight measurement should be used.

Dose preparation and administration should be performed using sterile, non-pyrogenic disposable materials including, but not restricted to syringes, needles, transfer tubing, and stopcocks.

Sebelipase alfa is a protein and should be handled and mixed gently to prevent foaming, as this has been associated with post-translational modification to other therapeutic proteins.

Prior to administration, the admixture should be inspected visually for particulate matter and discoloration. The contents should NOT be heated using a microwave or other heat source.

Sebelipase alfa should be diluted to a concentration of 0.1 to 1.5 mg/ml for infusion. Refer to the IMP manual for detailed instructions regarding preparation.

6.5.2 Administration of IMP

Sebelipase alfa should not be infused with other products in the same infusion tubing as the compatibility in solution with other products has not been evaluated. IMP infusions will be administered at an infusion rate depending on the subject's weight, and must be administered

Page 36 of 76

under close supervision of the Investigator, or designee. Sebelipase alfa should not be administered at an infusion rate exceeding 4 ml/kg/hr. Refer to the IMP manual for detailed instructions regarding administration.

